3.1 Trial design

The CLASSIC trial is an investigator-initiated, international multi-centre, parallel-grouped, open-labelled, centrally randomised, stratified, outcome assessor- and analyst-blinded trial with adequate generation of allocation sequence, and allocation concealment.

3.2 Randomisation

Patients with septic shock fulfilling the inclusion criteria will be randomised if they do not fulfil an exclusion criterion. The 1:1 randomisation will be centralised and web-based according to the computer-generated allocation sequence list, stratification variables (haematological or metastatic cancer (Y/N) and trial site), and varying block size at Copenhagen Trial Unit (CTU). The allocation sequence list will exclusively be known to the data manager at CTU and will be unknown to the investigators to allow immediate and concealed allocation to one of the two intervention groups. Each participant will be allocated a unique patient-screening number.

3.3 Blinding

Fluid restriction vs standard care fluid therapy cannot be blinded for investigators, clinical staff or participants. We will mask the allocation for the research staff who assess the long-term outcomes and for the trial statistician. Also, the management committee will write two abstracts based on the statistical report with the group allocation masked, one assuming the experimental intervention group is X and the control intervention group is Y, and one assuming the opposite. After this the allocation code will be unmasked [33, 34].

3.4 Participant timeline

We will strive to enrol patients as soon as they fulfil the inclusion criteria. The participants will continue the allocated intervention until they are discharged from the ICU with a maximum of 90 days after randomisation. If the participant is readmitted to the ICU within 90 days after randomisation, she/he will continue the allocated fluid therapy.

We will follow the participants for 1-year after randomisation and identify 1-year survivors in hospital, regional or national registries. We will contact all 1-year survivors approximately 2 weeks after to assess health related quality of life and cognitive function by interview.

The CLASSIC trial protocol Page 21/82

3.5 End of trial

The trial will end when the last patient enrolled has completed 1 year follow-up (last-patient-last visit). We will contact the last patient approximately 2 weeks after the 1-year follow-up date and allow 1 month of response time for the 1-year follow-up.

We will report the end-of-trial no later than 90 after last patient last visit to the Danish Medicines Agency and Ethics Committee.

4 Selection of participants

All patients admitted or planned to be admitted to an active trial site will be considered for participation. Patients will be eligible, if they comply with the inclusion and exclusion criteria below. We aim to include the patients as early as possible and exclude patients who may have specific fluid needs.

4.1 Inclusion criteria

All the following criteria must be fulfilled:

- Aged 18 years or above
- Admitted to the ICU or plan to be admitted to the ICU regardless of trial participation
- Septic shock defined according to the Sepsis-3 criteria [9]:
 - Suspected or confirmed site of infection or positive blood culture AND
 - Ongoing infusion of vasopressor/inotrope agent to maintain a mean arterial blood pressure of 65 mmHg or above AND
 - Lactate of 2 mmol/L or above in any plasma sample performed within the last
 3-hours
- Have received at least 1 L of IV fluid (crystalloids, colloids or blood products) in the last 24-hours prior to screening.

4.2 Exclusion criteria

We will exclude patients who fulfil any of the following criteria:

- Septic shock for more than 12 hours at the time of screening because we want to include patients early in their course
- Life-threatening bleeding as these patients need specific fluid/blood product strategies
- Acute burn injury of more than 10% of the body surface area as these patients need a specific fluid strategy
- Known pregnancy (details presented in Appendix 2)
- Consent not obtainable as per the model approved for the specific site.

We will not exclude patients enrolled in other interventional trials unless the protocols of the two trials collide; we present the rational for this in Appendix 7. Co-enrolment agreements will be established with the sponsor/investigator to maintain an updated list of trials approved for co-enrolment (Appendix 7).

The CLASSIC trial protocol Page 22/82

4.3 Participant discontinuation and withdrawal

The procedure of handling withdrawal of consent from a participant will follow national regulations for each participating country.

4.3.1 Discontinuation and withdrawal at the choice of the participant or the proxy

A participant, who no longer wishes to participate in the trial, can withdraw his/her consent at any time without need of further explanation, and without consequences for further treatment. For incompetent participants, consent can be withdrawn at any time by the person(s), who has given proxy-consent. To limit the amount of missing data, we will collect as much data as possible from each participant. Therefore, if possible, the investigator will ask the participant or the proxy to which extent the withdrawal includes:

- receiving the trial intervention only (allowing for all data registration and follow-up)
 OR
- receiving the trial intervention AND further registration of daily data and/or follow-up

Only the participant can demand deletion of already registered data and only if the participant did not consent previously. If so, the data will be deleted, and a new participant will be enrolled to obtain the full sample size.

4.3.2 Discontinuation and withdrawal at the choice of the investigator

A participant may have the intervention stopped by the clinician or investigator at any time, if:

- The participant experiences intolerable adverse reactions or events (including SAR or SUSAR) suspected to be related to the trial intervention.
- The clinicians in conjunction with the coordinating investigator decide it to be in the interest of the participant
- The participant after inclusion is subject to involuntary hospitalization, the intervention will stop.

In these cases, the collection of data and the follow-up will continue, and the participant will remain in the intention-to-treat population.

4.3.3 Discharge to another ICU

Participants who are discharged to another ICU will be regarded as discharged from the ICU unless the receiving ICU is an active CLASSIC trial site. If so, the participant will continue the allocated intervention at the new trial site until discharge from ICU. Participants referred to intermediate or step-up/step-down beds cared for by ICU staff trained in the CLASSIC trial protocol will continue the allocated intervention.

The CLASSIC trial protocol Page 23/82

5 Selection of trial sites and personnel

5.1 Trial sites and setting

Trial sites will be ICUs in Europe and potentially in Canada and Australasia where we explore the possibilities for collaboration. Trial sites are listed in the section Administrative information (p. 3). This section will be updated during the trial.

5.2 Trial personnel

All doctors caring for patients in participating ICUs will be eligible to enrol patients in the trial and all clinicians caring for patients will be eligible to care for and perform the interventions in the trial participants. All participating ICUs will receive written and oral instructions about the trial procedures. A 24-hour hotline will be available for trial-related questions.

6 Trial interventions

The intervention period is the entire ICU admission to a maximum of 90 days.

6.1 Experimental intervention

No IV fluids should be given unless one of the below extenuating circumstances occurs; in these cases, IV fluid may be given in measured amounts:

- In case of severe hypoperfusion or severe circulatory impairment defined by either:
 - Lactate 4 mmol/L or above
 - Mean arterial blood pressure below 50 mmHg (with or without vasopressor/inotrope)
 - Mottling beyond the kneecap (mottling score >2) OR
 - Urinary output less 0.1 mL/kg bodyweight/h, but only in the first 2 hrs after randomisation

A bolus of 250-500 ml of IV crystalloid solution may be given followed by re-evaluation. These criteria identify patients at increased risk of death [35, 36, 37], and were found feasible and not associated with harm in the CLASSIC pilot trial [5].

- In case of overt fluid losses (e.g. vomiting, large aspirates, diarrhoea, drain losses, bleeding or ascites tap) IV fluid may be given to correct for the loss, but not above the volume lost.
- In case the oral/enteral route for water or electrolyte solutions is contraindicated or has failed as judged by the clinical team, IV fluids may be given to:
 - Correct dehydration or electrolyte deficiencies.
 - Ensure a total fluid input of 1 L per 24 h (fluids with medications and nutrition counts as input).

IV fluids may be given as carrier for medication, but the volume should be reduced to the lowest possible volume for the given medication.

6.2 Control intervention

There will be no upper limit for the use of either IV or oral/enteral fluids. In particular:

The CLASSIC trial protocol Page 24/82

- IV fluids should be given in the case of hypoperfusion or circulatory impairment and should be continued as long as hemodynamic variables improve including static or dynamic variable(s) as chosen by the clinicians. These criteria are based on the SSC guideline [11]
- IV fluids should be given as maintenance if the ICU has a protocol recommending maintenance fluid
- IV fluids should be given to substitute expected or observed loss, dehydration or electrolyte derangements

6.3 Co-interventions

Types of fluid to be used in both intervention groups:

- IV fluids given for circulatory impairment: Only isotonic crystalloids are to be used as per the Scandinavian guideline for fluid resuscitation [38]
- Fluids given to substitute overt loss: Isotonic crystalloids are to be used. If large amounts of ascites are tapped, then human albumin may be used [39]
- Fluids used for dehydration: Water or isotonic glucose should be used
- Fluids used for electrolyte disturbances: Fluids should be chosen to substitute the specific deficiency, including water in the case of severe hypernatremia
- Blood products are only to be used on specific indications including severe bleeding, severe anaemia and prophylactic in case of severe coagulopathy.

6.4 Concomitant interventions

The use of concomitant interventions for septic shock should be based on the updated international sepsis guidelines [11]. In particular, we suggest the following to trial sites:

- Relevant antibiotics and source control for the infection
- Noradrenalin as vasopressor
- Renal replacement therapy based on conservative criteria [40] (i.e. severe hyperkalaemia (p-K > 6.0 mmol/L), severe metabolic acidosis (s-bicarbonate < 10 mmol/L and pH < 7.20), persistent kidney injury >72 h (oliguria/anuria or s-creatinine has not declined to 50% of the peak), or severe fluid overload combined with hypoxic respiratory failure (P/F-ratio < (26 kPa (200 mmHg)).

6.5 Criteria for modification of interventions for a given trial participant

The clinical team may at any time violate the protocol if they find it to be in the best interest of the participant. We will have a CLASSIC trial hotline to enable discussion around the clock between the clinicians caring for trial participants and the CLASSIC trial team regarding protocol related issues.

6.6 Assessment of participant compliance

We will monitor protocol compliance at the trial site through the electronic case report form (eCRF) and alert trial sites in the case of clear violation (central monitoring). In addition, the trial will be externally monitored according to the GCP directive and the monitoring plan (section 11).

The CLASSIC trial protocol Page 25/82

7 Outcome measures

7.1 Primary outcome

All-cause mortality at day 90 after randomisation

7.2 Secondary outcomes

- Number of participants with one or more serious adverse events (SAEs) in the ICU defined as ischaemic events (cerebral, cardiac, intestinal or limb ischaemia) or as a new episode of severe acute kidney injury (modified KDIGO3 [41])
- Number of participants with one or more serious adverse reactions (SARs) to IV crystalloids in the ICU as defined in section 8.2
- Days alive at day 90 without life support (vasopressor / inotropic support, invasive mechanical ventilation or renal replacement therapy)
- Days alive and out of hospital at day 90
- All-cause mortality at 1-year after randomisation
- HRQoL 1-year after randomisation measured using the EuroQoL (EQ)-5D-5L and EQ-VAS scores. Participants who have died will be assigned the lowest possible scores
- Cognitive function 1-year after randomisation as assessed by the Montreal Cognitive Assessment (MoCa) score

Several of the secondary outcomes above are composite outcomes. The single components of these will also be analysed and presented in a supplement to the primary publication.

8 Safety

8.1 Definitions

In the CLASSIC trial, we will use the definitions bellow [42].

Adverse Event (AE): any undesirable medical event occurring to a participant during a clinical trial, which does not necessarily have a causal relationship with the intervention.

Adverse Reaction (AR): any undesirable and unintended medical response related to the intervention occurring to a participant during a clinical trial.

Serious Adverse Event (SAE): any adverse event that results in death, is life-threatening, requires hospitalisation or prolongation of existing hospitalisation, results in persistent or significant disability or incapacity, or is a congenital anomaly or birth defect.

Serious Adverse Reaction (SAR): any adverse reaction that results in death, is life-threatening, requires hospitalisation or prolongation of existing hospitalisation, results in persistent or significant disability or incapacity, or is a congenital anomaly or birth defect.

The CLASSIC trial protocol Page 26/82

Suspected Unexpected Serious Adverse Reaction (SUSAR): any suspected adverse reaction which is both serious and unexpected (the nature or severity of which is not consistent with the information available to date).

8.2 Risk and safety issues in the CLASSIC trial

The trial participants will all be ICU patients for whom all adverse events and reactions are documented routinely in the patient health record (i.e. ICU notes, charges and laboratory reports). We will record in the eCRF the occurrence of SAEs and SARs on all trial days in ICU for all included patients and report SAEs and SARs as outcomes measures.

Both interventions groups will receive IV crystalloids as part of the protocol. We have identified the SARs to these fluids in the Danish Summary of Product Characteristics (SPCs) as listed below. The adverse reactions to the crystalloid solution not registered in the CLASSIC trial are listed in Appendix 3 including the reasoning.

SARs to crystalloid solutions (isotonic saline and buffered solutions (Ringer's lactate, Ringer's acetate and PlasmaLyte™)) assessed in the CLASSIC trial

- Generalised tonic-clonic seizures
- Anaphylactic reactions
- Central pontine myelinolysis
- Severe hypernatremia (defined as p-Na > 159 mmol/L)
- Severe hyperchloraemic acidosis (defined as pH < 7.15 AND p-chloride > 115 mmol/L)
- Severe metabolic alkalosis (defined as pH > 7.59 AND SBE > 9 mmol/L)

8.3 Assessment of adverse events

8.3.1 Timing

In all participants, we will assess the occurrence of SAEs and SARs on all trial days the participants spend in ICU to a maximum of 90 days.

8.3.2 Classification of an event

We will make no inferences about a causal relationship between the intervention and the event/reaction of the SAEs (7.2) and SARs (8.2), but register the occurrence in the two groups and report them in the final report according to the definition given above. As for any other SAE not covered in section 7.2 and 8.2, the investigators will report them if they are adjudicated to be related to the trial intervention to Sponsor or his delegate within 24 hours. If such a SAE is deemed related to the intervention by Sponsor and the investigator, it will be considered a SUSAR and reported as such (section 8.4).

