8.4 Reporting

Any serious adverse reaction/event not covered in the secondary outcomes (defined in 7.2 and 8.2) adjudicated to be related to the trial intervention by the investigator, will be reported within 24

The CLASSIC trial protocol Page 27/82

hours to the Sponsor or his delegate. If deemed a SUSAR by the Sponsor, he will report it to the Danish Medicine Agency within 7 days after the report of a life-threatening or fatal SUSAR. No later than 8 days after the reporting, the Sponsor will inform the Danish Medicines Agency of relevant information on the Sponsor's and the investigator's follow-up action to the life-threatening or fatal SUSAR. Any other SUSARs will be reported to the Danish Medicines Agency no later than 15 days from the time when the Sponsor is informed.

Once a year, the Sponsor will submit a list of all SARs that have occurred at all sites during the trial period and a report on safety of the trial subjects to the Danish Medicines Agency.

The Sponsor will notify the Danish Medicines Agency when the trial has been completed (no later than 90 days thereafter) and if earlier than planned, the reasons for stopping the trial.

In addition, we will report all SAEs and SARs defined in 7.2 and 8.2 as outcome measures and all SUSARs in the final trial report and the results of the trial will be reported on EudraCT.

9 Procedures, assessments and data collection

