The DMSC will prepare minutes of their meetings. The closed minutes will describe the proceedings from all sessions of the DMSC meeting, including the listing of recommendations by the committee. Because it is possible that these minutes may contain unblinded information, it is important that they are not made available to anyone outside the DMSC.

The CLASSIC trial protocol Page 56/82

Recommendations to the Management Committee

The planned interim analyses will be conducted after participant no. 155 and no. 466 has been followed for 30 days and again when no. 777 has been followed for 90 days.

After the interim analysis meetings, the DMSC will make a recommendation to the MC to make extraordinary efforts to enforce protocol adherence (1st and 2nd interim analyses) and continue, hold or terminate the trial (3rd interim analysis).

The independent DMSC will recommend pausing or stopping the trial if group-difference in the primary outcome measure, SARs or SUSARs is found at the interim analyses with statistical significance levels adjusted according to the Lan DeMets group sequential monitoring boundaries based on O'Brien Fleming alfa-spending function. If the recommendation is to stop the trial the DSMC will discuss and recommend on whether the final decision to stop the trial will be made after the analysis of all participants included at the time (including participants randomized after participant number 777) and whether a moratorium shall take place (setting the trial at hold) in the further inclusion of participants during these extra analyses. If further analyses of the participants included after 777 participants is recommended the rules for finally recommending stopping of the trial should obey the Lan DeMets stopping boundary.

Furthermore, the DMSC can recommend pausing or stopping the trial if continued conduct of the trial clearly compromises participant safety. However, stopping for futility to show an intervention effect of 15% RRR (or RRI) for mortality will not be an option as intervention effects less than these may be clinically relevant as well.

This recommendation will be based primarily on safety and efficacy considerations and will be guided by statistical monitoring guidelines defined in this charter and the trial protocol.

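### For unlisted serious events, sections 8.3.2 and 8.4 let the sponsor's disagreement alone override the investigator's suspicion, which does not fit the SUSAR definition in section 8.1

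*Protocol*

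**What the plan says.** Protocol section 8.1 defines a SUSAR as "any suspected adverse reaction which is both serious and unexpected", where unexpected means that its nature or severity does not fit the information available to date.

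Section 8.3.2 deals with serious adverse events not covered by sections 7.2 and 8.2. Of these it says that "the investigators will report them if they are adjudicated to be related to the trial intervention to Sponsor or his delegate within 24 hours". The rule that follows is that, when "deemed related to the intervention by Sponsor and the investigator, it will be considered a SUSAR".

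The same sequence is repeated in section 8.4. An unlisted event that the investigator has adjudicated related goes to the sponsor inside a day, and then: "If deemed a SUSAR by the Sponsor, he will report it to the Danish Medicine Agency within 7 days" if it is fatal or life-threatening. Other SUSARs have a 15-day limit. Section 8.4 also commits the final trial report to listing all SUSARs.

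The DMSC charter (Appendix 4) provides for a recommendation to pause or stop if a "group-difference in the primary outcome measure, SARs or SUSARs is found at the interim analyses", judged against the Lan-DeMets boundaries. The SAP (Interim analyses) says the same.

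The Swedish appendix (14.5.1) has its own rule. An SAE missing from the RSI counts as unexpected and is reported as a SUSAR. It mentions no relatedness judgement by either party.

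**The concern.** Section 8.1 works on suspicion. Section 8.3.2 asks for two concurring judgements of relatedness, and section 8.4 gives the sponsor the second one. A treating investigator who has adjudicated an event related plainly suspects a reaction. If the sponsor disagrees, the main text has no further route by which the event reaches the agency on the 7- or 15-day clock or enters the SUSAR listing in the final report.

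Unlisted events also have little other cover. The daily form in section 9.2.2 has yes/no fields for four ischaemic events and six SARs, plus creatinine and renal replacement therapy, and none for any other serious event. The classification rule therefore largely decides whether such an event is seen outside the site. The trial is open-label, and the sponsor sits on the Management Committee that takes the final stopping decision. That is a structural reason for not leaving the decision to one party, and it implies nothing about conduct.

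**Working it through.** No calculation applies: the plan states no figure here and the point depends on no rate or sample size. The check is to compare the rules.

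**1. Outcome of each combination of judgements (8.3.2 and 8.4).**

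| Investigator: related? | Sponsor: related? | Main-text result |
|---|---|---|
| Yes | Yes | SUSAR, expedited report |
| Yes | No | No SUSAR, no expedited report |
| No | Yes | Event is not sent to the sponsor, so no report |
| No | No | No report |

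One of the four combinations leads to an expedited report. The second row is the defect: the investigator's adjudication meets the suspicion element of 8.1, and the event is still not classified. The third row hardly arises under the main text, because the sponsor sees an unlisted event only after it has been adjudicated related.

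**2. Criteria compared.** Section 8.1 requires suspicion, seriousness and unexpectedness. Section 8.3.2 requires seriousness and two relatedness judgements, and does not ask about unexpectedness. It can therefore be too broad as well as too narrow. Appendix 3 gives an example: heart failure and pulmonary oedema are listed reactions to Ringer's acetate that the trial does not register directly. A serious case that both parties deem related would be a SUSAR under 8.3.2. Under 8.1 it would first have to be unexpected in nature or severity.

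**3. Sweden.** Section 14.5.1 turns on RSI listing alone. The same unlisted event could be reported as a SUSAR from a Swedish site and not from a Danish one. The protocol thus holds three rules that do not match: 8.1, 8.3.2 with 8.4, and 14.5.1.

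**4. Monitoring.** The charter's file for the third interim analysis has eight variables: identifier, group code, two fluid volumes, protocol violations, 90-day mortality, an SAE indicator and a SAR indicator. None is a SUSAR variable. The stopping ground that names SUSARs has no routine data behind it, whichever classification rule applies.

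**The case against.** The case on the other side has several sound parts.

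- Section 8.1 does not say whose suspicion counts, so 8.3.2 could be read as assigning that judgement. This stands in part: the conflict is about the threshold, and is not a flat contradiction over who decides. But a threshold of suspicion is still not the same as two concurring judgements of relatedness.
- Section 8.3.2 says if, not only if, and the sponsor's decision in 8.4 could concern unexpectedness alone. Read by itself, 8.4 allows that. Section 8.3.2 does not, since it names the sponsor's view of relatedness, and neither section gives another route.
- Much of the safety data is untouched. Ischaemic events, severe acute kidney injury and the six listed SARs are recorded in both groups without causal inference, and all-cause mortality is the primary outcome. The sponsor sends the agency a yearly list of SARs and a safety report. The DMSC can ask for event distributions at any time, and can recommend stopping on safety grounds without any boundary. All of this stands and limits the reach of the point. It does not restore the expedited report or the SUSAR listing.

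A reader might infer that every disagreement between investigator and sponsor loses an event throughout the trial. The Swedish rule and the separate recording of listed events show otherwise. A reader might also blame the joint rule for the lack of SUSAR data at the interim analyses, but that gap lies in the charter's file specification.

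**Conclusion.** The point holds as a defect in the stated rule. Followed exactly, 8.3.2 and 8.4 allow one party to withhold from expedited reporting an event that another party has already adjudicated related, and that would qualify under 8.1 if also serious and unexpected. Two further mismatches go with it: 8.3.2 omits unexpectedness, and Sweden has a different rule.

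The effect is limited to serious events outside 7.2 and 8.2 that are handled under the main-text rule. It does not touch the primary estimate or the listed safety outcomes. Its size cannot be derived, because the documents give neither the number of unlisted events nor how often the two parties disagree. It is tempting to assume that each party judges independently and to compare a both-must-agree rule with an either-suffices rule. The documents do not support that comparison. The judgements are sequential, the sponsor sees only events already adjudicated related, and the sponsor judges with the investigator's report in hand.

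The conclusion rests on one reading: that an investigator's adjudication of relatedness amounts to suspicion in the sense of 8.1. It is worth correcting, as a moderate rather than a critical point.

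**What to change.** - In 8.3.2 and 8.4, state that a relatedness judgement by the investigator or the sponsor is sufficient, so that the sponsor cannot overrule the investigator's suspicion. State that the event is then a SUSAR if it is also serious and unexpected as in 8.1, and that both opinions are recorded.
- Reconcile section 14.5.1 with this rule, or say explicitly that Sweden differs and how its reports will be combined with the rest.
- Add SUSARs by group to the DMSC data, since the charter and the SAP name them as a ground for pausing or stopping.
- For the final report, list any event that an investigator adjudicated related but that was not classed as a SUSAR, with both opinions. The investigators' 24-hour reports should identify these.

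The cost is a short amendment to three protocol sections, one more variable in the interim file, and a few more expedited reports. No new reporting route is needed to remove the sponsor's veto, because the investigator's report already goes to the sponsor within 24 hours.
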